10.10 Treatment Compliance

The three required study treatments will be administered by the treating investigator. Potential deviations from the defined study-treatment administration will be reported as protocol deviations.

10.11 Duration of Study

Subjects will have a screening period of up to 10 days. All enrolled subjects will participate for a maximum duration of 84 weeks (\pm 14 days).

In the event of a public health emergency the study might be halted, recruitment interrupted, and/or study processes and flow might be modified impacting the study duration and/or visit schedule depending on the study status at the time of the event. Mitigations may include, but are not limited to, extending visit windows, performing visits by phone or video, and/or performing effectiveness assessments remotely (see Section 11.1.3).

11 STUDY PROCEDURES

11.1 Visit Schedule

The investigation activities and visit schedule are detailed in the Schedule of Events

The purpose of the screening visit (Visit 1) is to determine subject eligibility for participation in this study and must be completed -10 to -3 days prior to Day 1 (Visit 2). Eligible subjects will be randomized at the screening visit.

Subjects randomized to Group A will receive treatment at Day 1, Week 6, and Week 12. Group A subjects also have the option for one additional retreatment at Week 36. Subjects randomized to Group B will remain untreated until Week 24, when the primary effectiveness endpoint will be evaluated. Upon completion of all primary effectiveness assessments, Group B subjects will be treated (i.e., will receive delayed treatment) at Weeks 24, 30, and 36. Group B subjects will not be offered an additional retreatment.

All treatments should be administered at the study site by the treating investigator, occurring only after completion of all required pre-injection procedures and assessments.

Safety follow-up will occur until Week 84 ± 14 days.

The primary endpoint visit will occur at Week 24 (± 7 days)

In the case of premature discontinuation of the study, a final assessment (End of main period visit) should be performed.

11.1.1 Scheduled Visits

All scheduled visits and applicable study assessments must occur as noted in Section 11.1 and the Schedule of Events

11.1.2 Unscheduled Visits

To ensure subject safety, any subject who, for any reason, requires additional follow-up that does not coincide with a scheduled study visit should have that visit recorded as an unscheduled visit, during which concomitant medication/procedures, skin examination, and AEs must be assessed and recorded.

An unscheduled visit must be scheduled if entries in the subject diary require additional follow-up as determined by the investigator.

An unscheduled visit must be scheduled if information acquired from a subject during a post-treatment phone call requires additional follow-up as determined by the investigator.

11.1.3 Modified Visit Schedule during a Pandemic

In the event of a pandemic disease outbreak (e.g., new COVID-19 public health emergency), the sponsor's primary goal is to ensure the safety and well-being of participating subjects. In general, the following recommendations apply if a pandemic disease outbreak occurs:

[figure not shown]
- In general, limit scheduled visits to those necessary for subject safety, clinical care, or follow-up of AEs.
- Use phone or virtual study visits for routine, mandated safety follow-up visits as described in the study protocol.
- Determine if effectiveness data can be collected remotely.
- Exercise flexibility when necessary and possible to continue performing protocol required procedures (e.g., subject imaging, photography, if applicable).

11.2 Study Assessments and Definitions

[figure not shown]
11.2.1 Effectiveness Assessments

[figure not shown]
The effectiveness of subdermal implantation of diluted Radiesse for the correction of moderate to severe wrinkles in the décolleté will be evaluated with several assessments. Refer to the respective endpoints (Section 7.2), visit schedule (Section 11.1), and Schedule of Events for additional information on the methods and timing of effectiveness assessments.

11.2.1.1 ^{CCI}

11.2.1.9 ^{CCI}

11.2.2 Safety Assessments

Standard safety assessments, including documentation of AEs and SAEs reported by the investigator throughout the study, will be evaluated.

Refer to the respective endpoints (Section 7.2.2), the Schedule of Events and the safety definitions (Section 12) for additional information on the safety assessments.

11.2.2.1 Adverse Events (AEs)/Serious Adverse Events (SAEs)

All AEs/SAEs reported by study subjects, investigators, or other study staff after the time of informed consent through end of study will be recorded, regardless of causality. The period of observation for an AE extends from signing of the ICF through the subject's last study visit. Additional information (e.g., definitions, reporting requirements) regarding AEs and SAEs is provided in Section 12.1 and Section 12.2, respectively.

[figure not shown]
Study subjects will be queried for the presence or absence of any visual symptoms at each follow-up visit

If visual symptoms are reported at a follow-up visit, subjects will undergo visual function assessments to potentially identify ophthalmic signs and/or symptoms that may represent ophthalmic-artery occlusion as detailed in Section 11.2.2.2.3.

11.2.2.2 CCI

11.2.2.2.1 CCI

CCI

11.2.2.2.3 ^{CCI}

[figure not shown]

[figure not shown]

11.2.2.2.3.2

11.2.2.2.3.3

[figure not shown]
11.2.2.2.3.4

[figure not shown]

11.2.2.2.4

11.2.3 Additional Data Collected

Data for other assessments will be collected as follows:

· Demographics and other baseline characteristics;

· Medical history/concomitant diseases; and

Previous and concomitant medications and non-drug treatments.

For time points of all other assessments, refer to

11.2.4 Appropriateness of Assessments

The MAS Décolleté Wrinkles scales are currently the only clinical instruments shown to be valid and highly reliable in clinical grading of décolleté wrinkles in both the "At Rest' and "Dynamic" positions.[38] Using a psychometric evaluation process, 13 expert raters scored two sets of photographs from subjects presenting with a broad spectrum of age-related décolleté changes (e.g., wrinkling). This analysis demonstrated that subject scores on both MAS Décolleté Wrinkles scales were positively correlated with subject age (actual and estimated) and the estimated degree of treatment effort needed to produce aesthetic improvement. Further, both MAS Décolleté Wrinkles scales demonstrated substantial degrees of intra- and inter-rater reliability in the pool of expert raters. These findings demonstrate that the MAS Décolleté Wrinkles scales are valid in terms of content and structure and establish a threshold for treatment benefit.

12 SAFETY DEFINITIONS AND REPORTING REQUIREMENTS

12.1 Definition of an Adverse Event (AE)

An AE is any untoward medical occurrence, unintended disease or injury, or untoward clinical sign (including abnormal laboratory findings) in subjects, users, or other persons, whether or not related to the IMD.

Note:

- 1. This definition includes events related to the IMD.
- 2. This definition includes events related to the procedures involved.
- 3. For users or other persons, this definition is restricted to events related to the IMD.

12.1.1 Details of an AE

The period of observation for an AE extends from when the ICF is signed until the subject's last study visit. Any medical occurrence between the time the ICF is signed and the first treatment with the IMD is an AE and has to be documented in the subject's file and in the AE eCRF. Any observed AE will be fully investigated, documented, and followed until the event is either resolved or adequately explained. In cases of surgical or diagnostic procedures, the condition/illness leading to such a procedure is considered the AE rather than the procedure itself. New AEs reported to the investigator during the observational period, after the last treatment with the IMD, must be documented, treated, and followed like all other AEs.

Pre-existing conditions noted in the medical history should not be reported as an AE, unless the condition worsens or the disease reoccurs during the reporting period. To determine whether a condition has worsened, it is compared to the subject's condition at screening.

Elective treatments planned before screening, and which are documented in the subject's source data, are usually not regarded as AEs. However, elective procedures should be postponed, if possible, until the subject completes their participation in the trial.

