13.4.2 Safety Analyses

All safety analyses will be performed on the SES.

All AEs and SAEs will be listed, including type, duration, severity, and relationship to the IMD.

Only TEAEs will be summarized using MedDRA preferred terms (PTs) within the system organ classes (SOCs). Safety analyses regarding TEAEs will be performed overall, for treatment Group A and Group B (delayed-treatment control) where appropriate.

Treatment-emergent AEs (TEAEs) are defined as AEs with onset or worsening at or after the first administration of study treatment. In this regard, an AE with onset prior to treatment that worsens at or after first administration of study treatment must be documented as a new TEAE with onset at the time of worsening.

[figure not shown]

All other AEs that do not follow the prior definitions will be considered non-TEAEs.

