6.2 Safety Analyses

All safety analyses will be performed on the SES, if not specified otherwise.

For interim and final analysis adverse events (AEs) will be coded according to the Medical Dictionary for Regulatory Activities (MedDRA) version in effect at the time the respective database is closed.

Treatment-emergent AEs (TEAEs) are defined as AEs with onset or worsening at or after the first administration of study treatment. In this regard, an AE with onset prior to treatment that worsens at or after first administration of study treatment must be documented as a new TEAE with onset at the time of worsening.

Only TEAEs will be summarized CCI using MedDRA preferred terms (PTs) within the system organ classes (SOCs).

[figure not shown]

[figure not shown]

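### Worsening of a pre-existing condition is judged against screening, 164 to 185 days before first injection in Group B, so a rebound after partial improvement cannot become a TEAE

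*Protocol*

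**What the plan says.** Protocol 12.1.1 excludes a pre-existing condition in the medical history from AE reporting "unless the condition worsens or the disease reoccurs during the reporting period". It then fixes how worsening is decided: "To determine whether a condition has worsened, it is compared to the subject's condition at screening". The sentence applies to both groups and makes no exception for delayed treatment.

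The same section covers the time before treatment: "Any medical occurrence between the time the ICF is signed and the first treatment with the IMD is an AE".

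Protocol 13.4.2 defines TEAEs as "AEs with onset or worsening at or after the first administration of study treatment", and adds that "an AE with onset prior to treatment that worsens at or after first administration of study treatment must be documented as a new TEAE". SAP 6.2 carries the same definition: "Treatment-emergent AEs (TEAEs) are defined as AEs with onset or worsening at or after the first administration of study treatment". Neither document states the condition against which worsening is measured for this purpose.

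Protocol 11.1 places screening 3 to 10 days before Day 1. Group A is first injected on Day 1. For the other arm, "Subjects randomized to Group B will remain untreated until Week 24", and the Week 24 visit has a window of 7 days either side.

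Related TEAEs are the secondary safety endpoint, summarized by group and in total on subjects treated at least once (Protocol 13.3 and 13.4.2.1, SAP 6.2.2).

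**The concern.** The recording rule and the endpoint look back to different moments. If the question is what happened after the first injection, the informative reference is the subject's state just before it. Section 12.1.1 uses the state at screening. In Group A the two nearly coincide. In Group B almost six months separate them, long enough for a fluctuating condition to have changed.

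The case at issue is a Group B subject with a medical-history condition that is moderate at screening, mild before the Week 24 injection and moderate again afterwards. Against screening it has not worsened. It never resolved, so the recurrence clause does not clearly apply. The site following 12.1.1 enters no AE.

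Two things are at stake. The loss happens at data entry, so no analysis step can recover the event, and in this scenario it runs only towards under-counting. It also falls mainly on the subjects whose delayed treatment is justified in Protocol 8.2 by the wish to enlarge the exposed group for safety data.

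**Working it through.** **1. The plan's own safety figure.** Protocol 13.1 states that an event with true incidence 1.5% will be seen at least once among 152 subjects with probability 89.9%. Check: 1 − (1 − 0.015)^152 = 1 − 0.985^152 = 0.8995. The figure is reproduced and is not in dispute. The 3:1 split also checks: 152 × 3/4 = 114 and 152 × 1/4 = 38.

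**2. Age of the reference at first injection.** Inputs from Protocol 11.1: screening 3 to 10 days before Day 1; first injection on Day 1 (Group A) or at Week 24 (Group B); Week 24 window ± 7 days. Week 24 is taken as 24 × 7 = 168 days after Day 1.

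| Group | Shortest gap | Longest gap |
|---|---|---|
| A | 3 days | 10 days |
| B, nominal Week 24 | 168 + 3 = 171 days | 168 + 10 = 178 days |
| B, with window | 168 − 7 + 3 = 164 days | 168 + 7 + 10 = 185 days |

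With the window, the Group B gap is 23.4 to 26.4 weeks.

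**3. What the rules capture in Group B after the Week 24 injection.**

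| Situation | Result under the text as written |
|---|---|
| New event after injection | AE and TEAE |
| Event that began between consent and first injection, then worsens | Already an AE; new TEAE under 13.4.2 |
| Pre-existing condition above its screening level after injection | AE under 12.1.1 |
| Pre-existing condition that resolved and came back | AE through the recurrence clause |
| Pre-existing condition that partly improved, then rebounded to no more than its screening level | Not an AE, so not a TEAE |

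Only the last row is a gap. The clause on occurrences before treatment does not close it, because partial improvement is not an untoward occurrence. The new-TEAE rule does not close it either, because it applies to something already classed as an AE.

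**4. A consistency check.** Suppose the same condition had begun the day after consent. It would be an AE, and on a plain reading its increase from mild to moderate after injection would be a new TEAE. The same flare is counted or not according to which side of consent the condition started. SAP 6.3 takes start of treatment, not screening, as the line between medical history and concomitant disease, and between previous and concomitant therapy.

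**5. Size.** Group B is 38/152 = 25% of randomized subjects. Its share of the safety set may be lower, because subjects who leave before Week 24 are never treated. The documents give no rate at which events would be missed. As an illustration only, take an event type that arises solely as such a rebound, with 1.5% incidence, and assume all 152 subjects are treated. With capture fraction c in Group B, the detection probability is 1 − 0.985^114 × (1 − 0.015c)^38:

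- c = 1: 89.9%
- c = 0.75: 88.4%
- c = 0.5: 86.6%
- c = 0 (Group A alone): 82.1%

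The last value is a floor under these assumptions, not an estimate.

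**The case against.** The strongest reply is that nothing here conflicts. Section 12.1.1 decides which pre-existing conditions become AEs, and 13.4.2 then decides which AEs are treatment-emergent. Both can be followed as written. This stands. A reader might infer that 12.1.1 violates the TEAE definition, but that definition fixes only when worsening happens and names no comparator state.

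A second reply is that most events are safe from the rule. This also stands. A reader might infer that post-injection flares in Group B generally go unrecorded, and the third table in the working shows otherwise. The usual injection-site reactions listed in Protocol 6.3, such as bruising, swelling and redness, would normally be new events. The protocol also leaves recurrence undefined, so some sites might report a rebound under that clause.

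Third, much text is not visible: part of the exclusion list, the restrictions section, the Schedule of Events and parts of the safety sections. Eligibility may keep out some relevant skin conditions, or a pre-injection examination may reset the reference. This lowers confidence. It does not remove the gap, because the sentence in 12.1.1 is complete and unqualified.

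Fourth, a reader might infer that the groups work under different detection rules. They do not: one rule applies to both, and only the age of the reference differs. Group A's later injections (Weeks 6 and 12, optionally Week 36) also fall well after screening.

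Finally, a screening reference protects against counting natural fluctuation. A chronic condition that happens to be mild at Week 24 and returns to its usual level would become a TEAE under a pre-injection reference. That is a real trade-off. Relatedness is already recorded for every AE, and the endpoint counts related TEAEs, so the means to separate the two exists.

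**Conclusion.** The point holds in a narrow form. The reference for worsening in 12.1.1 is not aligned with the treatment-emergent anchor in 13.4.2 and SAP 6.2. The mismatch is 3 to 10 days in Group A and 164 to 185 days in Group B. Its consequence is confined to medical-history conditions that partly improve before the Week 24 injection and then return to no more than their screening level.

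The number of such events is probably small and cannot be derived from the documents. No sample size, power or type I error statement depends on it. The conclusion assumes that sites apply 12.1.1 literally, that an incomplete improvement followed by a rebound is not treated as recurrence, and that no redacted rule supplies a later reference. This is a low-impact improvement, worth making because it is cheap and a missed entry cannot be recovered afterwards.

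**What to change.** Amend the sentence in Protocol 12.1.1 so that it has two parts. For events before the first injection, worsening is judged against screening, as now. For events at or after the first injection, it is judged against the subject's condition recorded immediately before that injection: Day 1 in Group A, Week 24 in Group B. Add matching eCRF completion guidance. The TEAE definitions in 13.4.2 and SAP 6.2 need no change.

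The cost is a short note on the status of ongoing conditions at a visit that already takes place, and possibly a few more reported TEAEs. Some of these will reflect natural fluctuation, which the existing relatedness assessment must separate from device effects. The change aligns the reference with the first injection only. It does not address partial improvement and rebound around later injections, which the TEAE definition does not anchor to either.

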12.1.2 Reporting and Handling of an AE

Data pertaining to AEs will be collected during each clinical study visit based on the subject's spontaneous description, through investigator inquiry, or upon discovery in the course of examinations completed during the visit. The investigator will assess and record any AE in detail in the subject file and on the AE eCRF. The following information must be recorded:

- AE diagnosis or main symptom;
- Affected treatment area: In case of a local reaction, the corresponding area should be reported;

- Date of onset;
- Intensity (maximum observed using the Severity Grading scale; see Section 12.1.3);
- Causal relationship to IMD (not related, related);
- Causal relationship to procedure (not related, related);
- Serious (yes or no), date serious since, and reason for seriousness;
- Outcome (see Section 12.1.5);
- AE leading to discontinuation of the clinical study (yes or no);
- Action taken with medical device; and
- Stop date.

In cases of a SAE (defined in Section 12.2), the investigator must also complete an SAE Report Form and report it to the sponsor within 24 hours, as described in Section 12.2.2.

12.1.3 Severity Grading for an AE

The clinical severity (i.e., intensity) of an AE will be classified as:

Mild: Signs and symptoms that can be easily tolerated. Symptoms can be ignored

and disappear when the subject is distracted.

Moderate: Signs and symptoms that cause discomfort and interfere with normal

functioning but are tolerable. They cannot be ignored and do not disappear

when the subject is distracted.

Severe: Signs and symptoms that affect usual daily activity and incapacitate the

subject, thereby interrupting her daily activities.

The investigator is required to grade the severity (i.e., intensity) of each AE.

12.1.4 Causal Relationship of an AE with an Investigational Medical Device

An AE is considered to be "related" to IMD or the treatment procedure if a causal relationship between the IMD or the treatment procedure and an AE is at least reasonably possible (i.e., the relationship cannot be ruled out). In this case, the non-serious event is considered an adverse device effect (ADE; Section 12.3). If the event is serious, it is a serious adverse device effect (SADE; Section 12.4).

The expression "reasonable causal relationship" is meant to convey that there are facts (evidence) or arguments to suggest a causal relationship. Otherwise, the relationship should be considered as "not related".

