12.3 Definition of an Adverse Device Effect (ADE)

An ADE is defined as an AE related to the use of an IMD.

Note:

- 1. This definition includes AEs resulting from insufficient or inadequate instructions for use, deployment, implantation, installation, or operation or any malfunction of the IMD.
- 2. This definition includes any event resulting from use error or from intentional misuse of the IMD.

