13.4.2.1 Secondary Safety Endpoints

Incidences of TEAEs related to the treatment with diluted Radiesse will be summarized by treatment group and total, overall and by study period by PT and SOC.

13.4.2.2 ^{CCI}

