5.2.2 Secondary Safety Endpoint

 Incidence of treatment emergent adverse events (TEAEs) related to treatment with diluted Radiesse, as reported by the treating investigator throughout the study.

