6.2.2 Secondary Safety Endpoints

Incidences of TEAEs related to the treatment with diluted Radiesse will be summarized by treatment group and total, overall and by treatment period by PT and SOC.

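### Does Protocol 12.1.4 give two conflicting tests for calling an adverse event related?

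*Protocol*

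**What the plan says.** Protocol 12.1.4 has two paragraphs. The first makes an event related to the device or the treatment procedure if a causal relationship is "at least reasonably possible (i.e., the relationship cannot be ruled out"). A related non-serious event is then an adverse device effect, and a related serious event is a serious adverse device effect. The second paragraph explains a reasonable causal relationship as one where "there are facts (evidence) or arguments to suggest a causal relationship", and closes with a default: "Otherwise, the relationship should be considered as" not related.

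The case report form takes a two-way answer, "Causal relationship to IMD (not related, related"), with a parallel item for the procedure (Protocol 12.1.2). Section 12.3 carries the label forward: "An ADE is defined as an AE related to the use of an IMD".

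The label feeds the one safety endpoint named in the visible text, the incidence of treatment-emergent events "related to treatment with diluted Radiesse, as reported by the treating investigator throughout the study" (SAP 5.2.2; likewise Protocol 7.2.2.1). Protocol 13.4.2.1 states: "Incidences of TEAEs related to the treatment with diluted Radiesse will be summarized by treatment group and total". SAP 6.2.2 has the same events "summarized by treatment group and total, overall and by treatment period by PT and SOC". The visible SAP text contains no definition of related of its own.

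**The concern.** Failing to exclude a cause is a weaker condition than having something that speaks for it. The first paragraph uses the weaker condition and joins it to reasonable possibility with an i.e., as if the two were the same. The second paragraph uses the stronger condition and adds a default in the opposite direction. The second paragraph also defines a phrase, reasonable causal relationship, that the first does not use, so the link between them has to be inferred.

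If both paragraphs are operative rules, two sites could follow the text faithfully and code the same borderline event differently. A two-way field would not show which rule was used. At stake would be the incidence of related treatment-emergent events, the split between adverse events and adverse device effects, and the reporting of serious events after the observational period, which under Protocol 12.2.2 depends on the investigator's view of relatedness.

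**Working it through.** The point turns on wording, so no sample-size or power formula applies. The one visible safety figure is the 89.9% chance of seeing at least once an event with true incidence 1.5% in 152 subjects (Protocol 13.1, SAP 3). It reproduces: 1 − (1 − 0.015)^152 = 0.8995. It concerns occurrence of an event, not its causality label, so it is unaffected here.

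**Step 1: the two paragraphs side by side.** Cross whether causation can be ruled out with whether any fact or argument supports it, and read each paragraph as a free-standing rule.

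| Ruled out? | Fact or argument? | First paragraph | Second paragraph |
|---|---|---|---|
| No | Yes | related | related |
| Yes | No | not related | not related |
| No | No | related | not related |
| Yes | Yes | not related | related |

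The rules agree in two cells. The fourth differs formally but has little practical content, since an event that has been ruled out is one whose supporting argument has been answered. The third cell is the real dispute.

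**Step 2: is the literal reading the natural one?** The criterion that the parenthesis explains is reasonable possibility. If not being ruled out meant strict logical exclusion, hardly any event in a treated subject could be excluded. Nearly every event would be related, and the not-related option in 12.1.2 would have almost no use. If it means that the link cannot reasonably be ruled out, an event with no fact or argument pointing to the device is one that reasonably can be. The second paragraph then says when that is so, and the two agree.

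**Step 3: how full is the disputed cell?** The second paragraph accepts facts or arguments and places no limit on the arguments. An investigator who hesitates to exclude the device normally has a reason: onset after injection, location in the treated area, or resemblance to the reactions listed in Protocol 6.3, which range from bruising and nodules to a long post-marketing list. Any of these is an argument and moves the event into the first row. What remains is an event for which the investigator has no reason to suspect the device and yet declines to exclude it. The documents give no count of such events, so no shift in incidence can be calculated.

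**Step 4: what depends on the label?**

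- All adverse events are recorded (Protocol 12.1.2) and listed with their relationship to the device (13.4.2). Summaries of treatment-emergent events are not restricted to related ones (Protocol 13.4.2, SAP 6.2).
- Serious events during the study are reported whether or not thought related, and the sponsor's product safety group evaluates them within 10 working days (12.2.2).
- Serious events after the observational period do depend on the label, but those reports generally stay out of the study database (12.2.2).
- The definition of an unanticipated adverse device effect (12.4.2) has its own causal wording and does not cite 12.1.4.
- No visible hypothesis test uses related events. Effectiveness and sample size are untouched.
- Training, investigator meetings and monitoring are planned to standardize sites (14.2.1), and medical and safety review can raise queries (14.2.2).

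**The case for a change.** The strongest case for a change starts from the endpoint. Related treatment-emergent events are the only safety endpoint named in the visible text, and safety is one of the two study objectives. The endpoint rests on the treating investigator's call, at up to ten sites. No untreated comparison would absorb inconsistent calls: the safety set holds only treated subjects (Protocol 13.3), and treatment emergence starts at first treatment, so Group B's events while untreated do not count unless they later worsen. The 84 weeks are meant to capture delayed and long-term events (Protocol 8.2), and late or non-local events are where the two paragraphs would most likely diverge. The text itself also invites the literal reading, through the i.e. in one paragraph and the default in the other.

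Part of this stands. The wording is loose, the phrases do not match, and the visible text does not say which paragraph prevails. Late events are the likeliest place for a difference. But none of it shows that the disputed cell holds more than an occasional event, and causality coding of late events rests on individual judgement under any single criterion.

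The obvious repairs also bring little. Deleting only the parenthesis leaves the second paragraph defining a phrase that the first does not use. Checking earlier borderline calls would need a way to find them, which a two-way field does not provide. It would also mean re-coding by investigators who know the treatment, which could itself bias the endpoint. A protocol modification further needs written ethics approval (14.6).

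**Conclusion.** No change to the plan is called for. This is a drafting looseness that investigators can resolve sensibly within the text as written. One of four logical combinations is in real dispute; it is probably very small, and no effect on the incidence of related treatment-emergent events is shown. Following Protocol 12.1.4 as it stands still gives a sound descriptive safety result, with complete event listings behind it.

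The conclusion rests on three assumptions: investigators read the parenthesis together with reasonable possibility and not as absolute exclusion; they treat timing, location and known reactions as arguments; and site training presents 12.1.4 as one standard. Parts of the safety sections are redacted, and 12.2.2 refers to a separate document on serious-event reporting, so the judgement covers the visible text only. If the protocol is reopened for another reason, aligning the two paragraphs on one phrase would be a harmless prospective edit, with no re-coding of events already assessed.
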